3 GENERAL CONSIDERATIONS FOR DATA ANALYSES

Statistical analyses will be performed by the Biostatistics unit of AIXIAL. Analyses will be conducted with SAS® software, version 9.4 (SAS Institute, North Caroline, USA).

Continuous data will be described in summary tables presenting, for each treatment group (and for the overall population for baseline descriptions), the number of non-missing observations (n), mean, standard deviation (SD), median, lower quartile (Q1), upper quartile (Q3), minimum and maximum, and 95% CI of the mean/median.

Categorical data will be described in summary tables presenting, for each treatment group (and for the overall population for baseline descriptions), the number of non-missing observations (n), count and percentage of each modality, and 95% CI.

95% CI of a proportion will be calculated using the scoring method of Wilson without continuity correction:

$$\text{Lower Limit} = \frac{2np + z^2 - z\sqrt{z^2 + 4npq}}{2(n + z^2)} \quad \text{Upper Limit} = \frac{2np + z^2 + z\sqrt{z^2 + 4npq}}{2(n + z^2)}$$

with n = number of non-missing observations

 p = percentage

 q = 1 - p

 z = 1.96 for two-sided 95%CI

Except for minimum and maximum, descriptive statistics will be presented with one more decimal than the recorded value.

For all variables, the number of missing values will also be reported in the tables, but they will not be counted for the percentage calculation (categorical data).

Variables recorded for each eye will be described separately for the worse eye and for the other eye (if applicable).

An eye is eligible if inclusion and exclusion (ophthalmological criteria) are respected at screening visit and baseline.

The worse eye is defined as the eligible eye with the highest IOP at baseline at 08:00. In case of no IOP difference between both eyes, the right eye will be considered the worse eye.

Quantitative parameters will be compared between groups using Mixed Model for Repeated Measures (MMRM) or Analysis of Covariance (ANCOVA) model. Assumptions underlying the MMRM (respectively ANCOVA for the sensitivity analyses) will be checked:

- A histogram of residuals will be plotted to check the assumption of normality
- The underlying assumptions of normality of residuals for mixed model will also be checked by using Skewness and Kurtosis statistics
- Normal probability plot and QQ-plot will be performed to check the assumption of normality
- Residuals will be plotted against predicted values to check the assumption of heteroscedasticity
- Plots of residuals and studentised residuals will be performed to detect outliers. Cook's distance will also be computed. If any outliers are detected, then main model will be performed with and then without them
- For ANCOVA models, Levene's test will also be performed to check the homogeneity of variances

For each model (MMRM or ANCOVA), if there is a strong violation of normality assumption (or violation of homogeneity of variances for ANCOVA), in addition to the initial model, a rank transformation will be done, and the model will be applied to ranks.

The acceptable risk of error for the statistical tests will be set at 5%, except for treatment by covariates interactions. For those interactions, the level of significance will be set at 7%.

For ordered qualitative variables, treatment groups will be compared using Cochran-Mantel-Haenszel (CMH) test stratified by country, with modified ridit scores and “row mean score differ” option.

Tables and Listings will be provided in separated documents except the listing of Deaths, Other Serious adverse events, discontinuations due to adverse events and other adverse events of special interest (see Section 7.10.3).

All individual data will be described in the listings 16.2, by treatment and by patient as follows: discontinued patients, protocol deviations, patients excluded from the efficacy analysis, demographic data, compliance, individual efficacy response data, adverse event listings, listing of individual laboratory measurements.

All individual data of eCRF will be described in the listing 16.4, by patient.

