						Topical ocular steroids and/ or topical ocular nonsteroidal anti-inflammatory drugs (NSAIDs)...
						Systemic immunosuppressive and systemic nonsteroidal anti-inflammatory drugs.....
						Any topical ocular treatments* (except long-term preservative-free lachrymal substitutes).....
						Contact lenses wear.....

* Prostaglandin monotherapy taken for at least 6 months by the patient has to be continued until the Screening Visit.

Patient Withdrawal	The investigator must choose to discontinue a patient for the following reasons: 
 • Adverse event(s) necessitating discontinuation from the study, • Lack of efficacy: if the patient or the investigator does not feel that the IP (T4032 or Lumigan®) has sufficiently controlled the pathology.
Efficacy Parameters	
 • IOP assessment with Goldmann applanation tonometer in each eye. Three time points in each eye (8:00; 10:00; 16:00) at Day 1, Week 6 and Week 12. • Efficacy assessment by the investigator at week 6 and week 12.

Safety Parameters	
 Assessment of the conjunctival hyperaemia on McMonnies photographic scale in each eye. Score of each ocular symptom throughout the day (irritation/burning, stinging, itching, tearing, eye dryness feeling, foreign body sensation) using 0-3 scale. Score of each ocular symptom upon instillation (irritation/burning, stinging, itching, tearing, eye dryness feeling, foreign body sensation) using 0-3 scale. Score of each ocular sign (blepharitis, eyelid oedema, iris pigmentation modification, abnormal eyelashes aspect, folliculo-papillary conjunctivitis) in each eye using 0-3 scale. Corneal fluorescein staining according to Oxford grading scheme in each eye. Far Best Corrected Visual Acuity in each eye. Ocular tolerance assessed by the investigator. Ocular tolerance assessed by the patient. Ocular AE reporting. Systemic AE reporting.
Primary Efficacy Endpoint	
The primary efficacy endpoint is the change from baseline (Day 1) to Week 12 in IOP at the three time points (8:00; 10:00; 16:00) in the worse eye.
 
The worse eye is defined as the eligible eye with the highest IOP at baseline at 8:00. In case of no IOP difference between both eyes, the right eye will be considered.

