4.2 Premature discontinuation and missing data

A patient who prematurely discontinues from the study should have, if possible, a premature discontinuation visit with the assessment planned on the final visit. This visit should take place as soon as possible after the patient stops taking the IMP.

For patients who prematurely discontinue from the study during the COVID-19 outbreak, the premature discontinuation visit was requested by visit on site if possible, else by phone.

For these patients who prematurely discontinue from the study, evaluations performed during the premature withdrawal visit will be considered as the first unobserved scheduled visit whatever their actual dates. If the premature withdrawal visit occurs after the discontinuation of the treatment, evaluations will be reviewed during the blind review meeting prior to the database lock to confirm their use thereof.

Otherwise, missing data will not be replaced, except for sensitivity analysis of the primary endpoint (see Section 6.1.2). Based on the Last Observation Carried Forward (LOCF) method, missing values at Week 12 will be replaced by the post-randomisation last available value. For the primary efficacy endpoint, a sensitivity analysis considering the post-randomisation last available value will be performed for the contralateral eye (see Section 6.2.1).

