6.2.2 Other analyses on IOP

Frequency distribution of patients with IOP <18 mmHg and IOP \geq 18 mmHg will be described by treatment group at each assessment time (Baseline [Day 1] at 08:00, 10:00 and 16:00, Week 6 at 08:00, 10:00 and 16:00 and Week 12 at 08:00, 10:00 and 16:00), separately for the worse eye and the contralateral eye.

Descriptive statistics will be performed on IOP at 08:00, 10:00 and 16:00 and on changes from baseline for the worse eye and for the contralateral eye at each assessment time (*i.e.*, baseline, Week 6 and Week 12), depending on the History of glaucoma or ocular hypertension.

Descriptive statistics will be performed on the mean diurnal IOP at baseline, Week 6 and Week 12. Change from baseline to Week 6 and change from baseline to Week 12 will be described.

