6.2.3 Global assessment of efficacy by the investigator

Global judgment of efficacy by investigator will be assessed on a 4-point ordinal scale (Very satisfactory, Satisfactory, Not very satisfactory, Unsatisfactory).

Assessment of Azopt® efficacy will be presented by frequency distribution for each modality and frequency distribution after regrouping 'very satisfactory' with 'satisfactory', and 'not very satisfactory' with 'unsatisfactory'.

Assessment of LT4032 or Lumigan® efficacy will be presented by frequency distribution for each modality and frequency distribution after regrouping 'very satisfactory' with 'satisfactory', and 'not very satisfactory' with 'unsatisfactory', at Week 6 and Week 12. After regrouping in 2 classes, comparison of treatment groups at Week 6 and Week 12 will be performed using a CMH test stratified by country.

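### The Week 12 efficacy rating and IOP <18 mmHg percentages leave out patients withdrawn for lack of efficacy whose last assessment is filed at Week 6, and no sensitivity analysis covers this

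*SAP*

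**What the plan says.** Four rules bear on this point.

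- Protocol synopsis, Patient Withdrawal. One of the two reasons for which the investigator must discontinue a patient is "Lack of efficacy: if the patient or the investigator does not feel that the IP (T4032 or Lumigan®) has sufficiently controlled the pathology".
- SAP 4.2. For a patient who leaves early, "evaluations performed during the premature withdrawal visit will be considered as the first unobserved scheduled visit whatever their actual dates". A visit held after treatment stopped is used only if the blind review confirms it.
- SAP 4.2. Otherwise "missing data will not be replaced, except for sensitivity analysis of the primary endpoint". SAP 6.2.1 extends LOCF to IOP change in the contralateral eye. No imputation is planned for a categorical efficacy outcome.
- SAP section 3. Missing values leave the denominator of every percentage: "they will not be counted for the percentage calculation (categorical data". Their count is still to be displayed, by table and by arm.

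Two outcomes are affected. SAP 1.3.2 lists the investigator's efficacy rating at Week 6 and Week 12 as a secondary endpoint. SAP 6.2.3 regroups it into two classes, and "comparison of treatment groups at Week 6 and Week 12 will be performed using a CMH test stratified by country". SAP 6.2.2 plans "Frequency distribution of patients with IOP <18 mmHg" and of its complement at each visit and time point, as description only.

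**The concern.** Withdrawal for lack of efficacy is informative about efficacy. Under these rules such a patient can be absent from the Week 12 denominator because treatment was judged not to be working. The Week 12 percentages then describe a group partly selected by outcome. If one product had more of these withdrawals, leaving them out would pull the arms together, and the Week 12 CMH test would not see the excess.

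SAP 6.1.2 plans analyses of the dropout pattern and its effect on the treatment comparison, but only for IOP change. The rating and the IOP classes have none. At stake is how a secondary endpoint and a descriptive responder table are read, in a trial whose aim is to show similarity.

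**Working it through.** **Who leaves the Week 12 denominator.** Applying SAP 4.2 case by case:

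- Exit visit before an attended Week 6 visit: filed at Week 6, nothing at Week 12. Excluded at Week 12.
- Week 6 attended, no usable later visit: nothing at Week 12. Excluded at Week 12.
- Week 6 attended, later usable exit visit: filed at Week 12. Included.
- No post-randomisation efficacy assessment at all: outside the m-ITT set (SAP 2.3), so not even in the missing row of the m-ITT tables.

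The point concerns the first two groups.

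**The plan's own figures.** The plan states no rate of lack-of-efficacy withdrawal and no expected success rate. Its sample-size figures (SAP 1.5) do reproduce. SE = 3 × √(2/180) = 0.316 and 1.5/0.316 − 1.96 = 2.78, giving 99.7% power per time point. Power for all three time points jointly is 99.3% at correlation 0.7, consistent with the stated figure of more than 90%. Also 360/0.9 = 400. None of this depends on the rating or the IOP classes.

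**Effect on the percentages.** Let N be patients per arm, w those withdrawn for lack of efficacy with no Week 12 value, and s the success proportion among the rest.

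- As written: s(N − w)/(N − w) = s.
- Withdrawals kept and counted as non-success: s(N − w)/N = s(1 − w/N).
- With equal s in both arms, the gap is 0 as written and s × (difference in w/N) when they are counted.

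Example with N = 180, s = 70% and 18 v 4 withdrawals (10% v 2%):

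- Successes: 0.70 × 162 ≈ 113 and 0.70 × 176 ≈ 123.
- As written: 113/162 = 69.8% v 123/176 = 69.9%.
- Counted: 113/180 = 62.8% v 123/180 = 68.3%, a gap of 5.6 points before rounding.

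Range over assumed s of 60%, 70% and 85%, and N of 180 (planned evaluable) or 242 (485 randomised, halved). Counts are rounded to whole patients, no other data are missing, and an unstratified chi-square stands in for the CMH test:

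| Withdrawals, arm A v arm B | Gap as written (points) | Gap when counted (points) | p when counted |
|---|---|---|---|
| 2% v 2% | 0 | 0 | 1.00 |
| 5% v 2% | at most 0.4 | 1.7-2.8 | 0.49-0.75 |
| 8% v 2% | at most 0.4 | 3.3-5.0 | 0.20-0.52 |
| 10% v 2% | at most 0.4 | 4.5-6.7 | 0.07-0.34 |
| 10% v 0% | at most 0.3 | 5.8-8.7 | 0.015-0.24 |
| 10% v 10% | 0 | 0 | 1.00 |

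The small gaps as written come from rounding to whole patients; their p-values are all 0.90 or higher. The same arithmetic applies to the IOP <18 mmHg percentage, which is not tested.

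**The case against.** A reader might infer that these patients vanish, that an excess of failures is hidden, or that the non-inferiority conclusion is biased. The documents support none of these.

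- Section 3 requires missing counts to be reported, and the shells of Tables 4.118 and 4.136 print n and a missing-data row by arm.
- SAP 5.1 tabulates discontinuations by arm and primary reason. Lack of efficacy has its own row in Table 1.25, repeated for the m-ITT set in Table 1.27, and Listing 1.3 gives each patient. A marked excess in one arm would be seen there.
- An exit visit filed at Week 6, if usable, enters the Week 6 rating and its CMH test, and the Week 6 IOP classes. An exit visit after an attended Week 6 counts at Week 12. It would be wrong to say that only patients without failure remain.
- Non-inferiority rests on IOP change by MMRM (SAP 6.1.1), which uses values filed at Week 6 and has LOCF and observed-case sensitivity analyses. The CMH test has no margin and supports no planned claim of similarity.
- An imbalance is hypothetical. No visit is scheduled between Day 1 and Week 6, and most of the assumed imbalances would not make the test significant.
- Lack of efficacy is a judgement, possibly the patient's, with no IOP threshold. Assigning such a patient to IOP ≥18 mmHg could contradict an exit reading below 18.

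All of this stands, and it limits the point. It does not close the gap. The missing row pools lack of efficacy with COVID-19, loss to follow-up and other reasons. Table 1.25 gives reasons but not timing relative to Week 6. A reader would have to rebuild the group from listings, and the Week 12 p-value would still exclude it.

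**Conclusion.** The point holds in a limited form. For a tested secondary endpoint and a descriptive responder table, the Week 12 percentages rest on a denominator partly selected by outcome, with no sensitivity analysis. An imbalance in lack-of-efficacy withdrawals without a Week 12 value would not appear in those percentages or in the Week 12 p-value.

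Under the assumptions above, the gap left out is about 1.7-2.8 points at 5% v 2% and about 4.5-6.7 points at 10% v 2%. Equal withdrawals lower the level in both arms but add no gap. The withdrawal and success rates are assumptions, so the documents do not show that any bias will occur or which arm it would favour. The primary conclusion and the sample size are unaffected. This is a low-cost improvement to secondary reporting.

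**What to change.** - **SAP 6.2.3.** Keep the observed-case analysis. Add a supportive Week 12 analysis (percentages and CMH test stratified by country) in which m-ITT patients withdrawn for lack of efficacy with no Week 12 rating stay in the denominator and count in the combined lower class (not very satisfactory plus unsatisfactory).
- **SAP 6.2.2.** Do not assign these patients an IOP class. Show them at Week 12 as a separate category, withdrawn for lack of efficacy with no Week 12 reading, kept in the denominator. The IOP <18 mmHg percentage then counts them as not achieving it.
- **Both sections.** Patients missing for other reasons, such as COVID-19, stay missing and are counted separately.

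The cost is a few lines of SAP text and one extra block or category in six existing tables (4.118-4.121, 4.136, 4.137). The reason for discontinuation is already planned for tabulation. The downside is slightly less favourable percentages, and a few patients classed without a Week 12 rating. Patients with no post-randomisation efficacy assessment remain outside the m-ITT set and would still be seen only in the discontinuation tables.

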3.1 Display of analysis results

The following labelling for treatment groups will be used in statistical tables: “T4032” and “Lumigan”.

3.2 Interim analyses

No interim analysis will be performed.

3.3 Centre effect management

For efficacy analysis, centre effect will not be tested, but country effect will be tested (Section 6.1.3).

3.4 Subgroup analyses

No subgroup analysis is planned except in case of statistically significant and qualitative treatment by covariate interaction.

3.5 Other strata and covariates

Country, wash-out duration factor and possible impact of COVID-19 pandemic will be included in all models as covariate, and CMH test used for ordered qualitative variables will be stratified by country.

Baseline value will be included in all MMRM and ANCOVA as covariate:

- For analyses on the change from baseline in IOP, baseline IOP will be included as covariate in MMRM and ANCOVA
- For analysis on the change from baseline in total symptoms score throughout the day, corresponding baseline value will be included as covariate in MMRM

3.6 Multiple comparisons and multiplicity

There is a single primary efficacy endpoint in the study (change from baseline in IOP at Week 12 in the worse eye) and non-inferiority will be achieved if the non-inferiority margin of 1.5 mmHg is met at each of the time point assessments: 08:00, 10:00 and 16:00. Other efficacy measures are defined as of secondary importance. Consequently, comparisons between T4032 and Lumigan® 0.01% will be performed at a two-sided significance level of 5% and no adjustment of the type I error rate will be made.

4 DATA HANDLING CONVENTIONS

4.1 Visit windows

All data will be organised and analysed according to the actual observed visits.

Moreover, for IOP, the recorded value should be allocated to the most appropriate time point.

Time point	Interval of time point
08:00	Until 09:00
10:00	From 9:01 to 13:00
16:00	From 13:01

If more than one record occurs within the same timepoint then the following rule should be applied: the closest non-missing result to the scheduled timepoint should be used. To be noted as the record not used will be reclassified in another timepoint if it occurs within 30min of interval of timepoint.

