All the ocular assessments have to be performed in both eyes.

- (1) Ocular symptoms (irritation/burning, stinging, itching, tearing, eye dryness feeling, foreign body sensation), scored using 0-3 scale, will be collected by the investigator /delegate.
- (2) At Screening Visit, one IOP measurement should be performed at 08:00 (\pm 30 minutes). At Day 1, Day 42/Week 6 and Day 84/Week 12, IOP should be measured at three time points: 08:00, 10:00 and 16:00 (each \pm 30 minutes) with a.m. measurements of IOP at least 2 hours apart. IOP measurements should be done at the same hours (\pm 30 min) than Day 1, by the same investigator and using the same technique (Goldmann applanation tonometer) for all visits.
- (3) To be performed if fundus examination / central corneal thickness measurement / automated visual field not done within the previous 12 months and/or results dating from the last 12 months not available.
- (4) To be performed only if the IOP is not stable at the Week 12 visit or if the ophthalmologist judges that it is necessary.
- (5) Azopt® must be stopped for 2 weeks before the Randomisation Visit.
- (6) Slit lamp examination: Score of each ocular sign (blepharitis, eyelid oedema, iris pigmentation modification, abnormal eyelashes aspect, folliculo-papillary conjunctivitis or other ocular abnormality) will be recorded in each eye using 0-3 scale.
- (7) Urinary test to be done for childbearing potential women.
- (8) Run-in treatment (Azopt®) will be instilled by the patient one drop in each eye twice a day (morning and evening) for 5 weeks.
- (9) One drop of IP (T4032 or Lumigan®) will be instilled by the patient in each eye once daily at 20:00 (\pm 1 hour) for 12 weeks.
- (10) Efficacy and ocular tolerance will be assessed by the investigator and the patient as very satisfactory, satisfactory, not very satisfactory, or unsatisfactory.
- (11) In case of AE, all treatments of the follow-up period will be collected.

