4.3.2 Baseline

Baseline will be defined for each assessment as an evaluation before the first instillation of the IMP:

- For IOP, the value recorded at 08:00 at Day 1, respectively at 10:00 and at 16:00, will be the baseline for analysis of IOP at 08:00, respectively at 10:00 and at 16:00
- For visual field, fundoscopy and corneal thickness, the value recorded at screening visit will be the baseline
- For others parameters, the value recorded at Day 1, will be the baseline for analysis

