6.1.1 Main analysis of the primary efficacy endpoint

The non-inferiority of T4032 to Lumigan® 0.01% on the change from baseline in IOP will be primarily tested using a MMRM approach. Three independent models will be performed, one for each time point (*i.e.*, at 08:00, 10:00 and 16:00). Each model will include as fixed factors, treatment, scheduled visit time point (Week 6 and Week 12), baseline IOP, wash-out duration, country as covariates, treatment by visit interaction, baseline IOP by visit interaction, and patient as random factor. The Restricted Maximum Likelihood (REML) estimation approach will be used, and the default covariance structure will be unstructured. Consistent with MMRM model fitting, no explicit imputation of missing assessments for a given visit time point will be performed. The 95% CI for treatment effect (difference T4032 - Lumigan® 0.01%) will be estimated at Week 12 in this model. Non-inferiority will be achieved if the upper bound of the 95% CI for the difference between treatment groups (T4032 - Lumigan® 0.01%) is lower than the margin of +1.5 mmHg for each of the three time points 08:00, 10:00 and 16:00.

The syntax with SAS using the MIXED procedure is detailed in [Appendix 1](#).

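### SAP 4.1 lets only the unused record change slot, so a first reading at 09:01 to 09:30 with the 2-hour gap kept stands as 10:00 and leaves 08:00 empty

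*SAP*

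**What the plan says.** SAP 4.1 (Visit windows) allocates each IOP record by the clock. The 08:00 slot takes anything up to 09:00, the 10:00 slot runs "From 9:01 to 13:00", and the 16:00 slot opens at 13:01. If two records share a slot, "the closest non-missing result to the scheduled timepoint should be used". One rescue follows: "the record not used will be reclassified in another timepoint if it occurs within 30min of interval of timepoint". Nothing in 4.1 keeps the readings in their planned order.

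Footnote 2 of the visit schedule (Protocol Table 2; SAP 1.2.2) sets the readings at 8:00, 10:00 and 16:00, each ±30 minutes, "with a.m. measurements of IOP at least 2 hours apart".

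The slots feed the primary analysis directly. Under SAP 4.3.2 "the value recorded at 08:00 at Day 1, respectively at 10:00 and at 16:00, will be the baseline" for the matching time point. SAP section 3 adds: "The worse eye is defined as the eligible eye with the highest IOP at baseline at 08:00". Under 6.1.1, non-inferiority is declared if the upper 95% confidence bound "is lower than the margin of +1.5 mmHg for each of the three time points 08:00, 10:00 and 16:00". In the same model, "no explicit imputation of missing assessments for a given visit time point will be performed".

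**The concern.** The rescue is attached to the wrong record. Take a patient who starts late and is read again two hours later. The record that could fill the empty 08:00 slot is the one 4.1 has already used at 10:00. The record that is free to move is too late to reach 08:00.

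At Week 6 or Week 12 the visit loses a measured 08:00 value, and the reading planned for 08:00 is analysed as 10:00. At Week 12 the LOCF sensitivity analysis (6.1.2) would then carry forward Week 6 in place of a value that was actually taken.

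On Day 1 the effect is wider. The 08:00 baseline is missing, so the patient has no 08:00 change from baseline, and mean diurnal IOP is missing too (4.3.13). The worse eye rests on the 08:00 baseline, and the only fallback covers equal pressures, so no eye can be assigned under the stated definition for any of the three models. If Day 1 was late and Week 12 on time, the 10:00 change also compares two different planned readings.

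**Working it through.** The plan states no figure on this point, so there is none to reproduce. The check runs the rule itself.

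**Inputs.** Slot limits, closest-record rule and 30-minute clause: SAP 4.1. Gap of at least 120 minutes and ±30-minute windows: footnote 2 of the schedule.

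**Which record wins the 10:00 slot.** Let the first reading be at 09:00 + x minutes, with x from 1 to 30, and the gap 120 + g minutes, with g ≥ 0.
- First reading: 60 − x minutes from 10:00.
- Second reading, at 11:00 + x + g: 60 + x + g minutes from 10:00.
- Difference: 2x + g, which is at least 2 minutes. The first reading always wins.

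| First / second | Minutes from 10:00 | Result under 4.1 |
|---|---|---|
| 09:00 / 11:00 | not needed | 08:00 and 10:00 both filled as planned |
| 09:01 / 11:01 | 59 v 61 | 09:01 used as 10:00; 11:01 dropped; 08:00 empty |
| 09:10 / 11:10 | 50 v 70 | 09:10 used as 10:00; 11:10 dropped; 08:00 empty |
| 09:30 / 11:30 | 30 v 90 | 09:30 used as 10:00; 11:30 dropped; 08:00 empty |
| 09:10 / 10:10 (gap not kept) | 50 v 10 | 10:10 used as 10:00; 09:10 moved to 08:00 |

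**Whether the loser can be rescued.** It is at 11:01 or later. The 08:00 slot plus 30 minutes ends at 09:30, so it cannot go there. The 16:00 slot less 30 minutes begins at 12:31, so a second morning reading cannot go there either. A second reading at 12:31 or later with no 16:00 record would move to 16:00, but that is no longer a morning reading, and 08:00 is still empty.

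**What the SAP's own limits accept.** 09:01 to 09:30 lies within 30 minutes of the 08:00 slot. 11:01 to 13:00 lies inside the 10:00 slot. Both readings are therefore acceptable in their planned places; only the order of the steps prevents it.

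**The wording of the 30-minute clause.** It could mean 30 minutes from a slot's interval or from its scheduled time. On the second meaning it could never act: 07:30–08:30, 09:30–10:30 and 15:30–16:30 each lie wholly inside their own slots. The interval meaning is the only one that gives the clause any effect. The present misallocation occurs on either meaning.

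**Enumeration.** Stepping by the minute, with the gap kept and the second reading before noon, starts from 09:01 to 09:30 give 59 + 58 + … + 30 = 1,335 pairs. They are part of a run over all starts after 09:00 in which 1,770 of 1,770 pairs behaved this way. With both readings inside the ±30-minute windows and the gap kept, 1,891 of 1,891 pairs were allocated correctly. These count clock combinations, not patients.

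**The case against.** The strongest reply is that the rule acts only on visits already off protocol. A first reading at 09:01 is more than 30 minutes past the first window, and with the gap kept the second is more than 30 minutes past its own. That stands, and it limits the point. It does not remove it, because 4.1 was written for off-schedule readings, and the primary m-ITT set does not exclude patients for such deviations.

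A second reply is that clock time matters for IOP. Every reading after 09:00 is nearer to 10:00 than to 08:00, so the SAP may prefer a well-timed 10:00 value to two late ones. This has force for late starts in general. Up to 09:30, however, the SAP has already decided otherwise: it accepts 09:10 as 08:00 when the other record is 10:10, and 11:10 as 10:00 when it stands alone. The same 09:10 reading changes label only because of when the second was taken.

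Three stronger readings are tempting, and the documents do not support them.
- A reader might infer that every start after 09:00 should be moved back to 08:00. The SAP gives no such tolerance beyond 09:30; moving 10:45 and 12:45 would put each value 165 minutes from its label.
- A reader might infer that compliant sites lose data and non-compliant ones keep it. The sites that lose data kept the gap but missed both ±30-minute windows.
- A reader might infer a biased treatment difference. The rule is the same in both arms, randomisation is stratified by site, and no shift is shown.

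**Conclusion.** Wrong as written, within a narrow range. For a first reading from 09:01 to 09:30 with the 2-hour gap kept, 4.1 always drops the second morning reading, uses the first as 10:00 and leaves 08:00 empty. Each affected visit loses one of its three IOP values and carries another under a different label. On Day 1 the worse eye is also undefined. The result rests on the literal text of 4.1.

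The number of such visits is not in the documents. A reader might assume that 1% to 5% of the 970 Day 1 and Week 12 visits (2 × 485 randomised) start after 09:00, giving about 10 to 49. That percentage has no source, and the count would be a ceiling: it needs every late start to fall by 09:30, every second reading to be delayed as well, and every patient to reach Week 12.

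Power is not the issue. With 180 per arm, SD 3 and margin 1.5, the standard error is 3 × √(2/180) = 0.316, and 1.5/0.316 − 1.96 = 2.78, or 99.7% power per time point (about 99.3% jointly at correlation 0.7). The case for change is that measured primary-endpoint data are lost without need and that a Day 1 case has no defined worse eye.

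**What to change.** Add to SAP 4.1: *If two records fall in the same slot and an adjacent slot is empty, whichever record lies within 30 minutes of the empty slot is assigned to it, and the other is kept in the original slot; the closest-record rule applies only if neither record qualifies.* State that the 30 minutes run from the slot's interval and, if both records qualify, that the one nearer the empty slot moves.

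Leave first readings after 09:30 under the existing rule and flag them as deviations. Settle at the blind review, before database lock, how the worse eye is assigned when the Day 1 08:00 slot is empty.

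The cost is one sentence and a small change to the derivation program. Visits inside the ±30-minute windows with the gap kept are unaffected. The downside is that a few 08:00 values will have been taken as late as 09:30, and their paired 10:00 values from 11:01 on. At 09:10 and 11:10 each is 70 minutes after its label, but the SAP's intervals already permit both.
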